5. Length of hospital stay and time (in days) to meeting discharge criteria. Often, patients remain inpatient beyond the time at which they first meet discharge criteria due to a variety of psychosocial factors. Thus, length of hospital stay and time (in days) to meeting discharge criteria will be separately recorded. Discharge eligible criteria include: (1) hemodynamically stable, (2) afebrile, (3) ROBF, (4) pain controlled with oral analgesics, (5) independence with ADLs, (6) walking greater than 250 feet.

6. Total intravenous fluids administered and time to postoperative diuresis defined as the time lapse from date of surgery (DOS) to a net negative fluid balance sustained over a 24 h time period.

7. Need for vasopressors (amount and duration).

8. Incidence of major postoperative complications, including 30-day hospital readmission.

9. Total direct costs associated with loco-regional anesthesia: The analysis will include the direct variable cost of supplies and pharmacy (including initiation of PCA in the event of block failure) as well as anesthesia professional fees (TEA only; both intraop and postop) and cost of OR time in minutes to perform the blocks.

10. Post-discharge narcotic utilization. Total outpatient narcotic use during the immediate outpatient postoperative period will be obtained from the patient by nurse phone survey on postoperative day 14, provided the patient is outpatient and not still admitted or readmitted to the hospital.

Translational Endpoints:

1. Biomarkers of surgical stress response. Blood samples (10mL of whole blood) will be collected on the DOS when routine IV access is established in preop or the operating room and postoperative days 1 through postoperative day 7 coinciding with routine IV access for blood, for analysis of peripheral blood counts. Blood collection on postoperative day 0 is optional. Serum will

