The study is powered for the primary outcome of Area under the Curve (AUC) for pain from 0-48 hours. From review of the literature of previous studies, we deemed a margin of 80% of 48 hours to be non-inferior [24,25,]. A group sample size of 50 per cohort is needed achieve a 90% power to detect non-inferiority using a one-sided, Mann-Whitney test. The margin of non-inferiority is 38 (80% of 48 hours). The non-inferiority margin corresponds to an increase in pain, not a decrease. The pain VAS ranges from 0 to 10, with 10 being the worst pain. Therefore, non-inferiority will be declared if the average AUC for liposomal bupivacaine is no more than 38 units compared to the average AUC in the TEA group. The true difference between the means is assumed to be 0.0. The significance level (alpha) of the test is 0.025 and the data are drawn from populations with standard deviations of 55.0. These assumptions were derived from previous Pacira studies. It is reasonable to assume that the standard deviation of the AUC for 0-48 hours is about 55 units and the difference between the groups is 0. Sample size calculations were performed using PASS (PASS 16 Power Analysis and Sample Size Software (2018). NCSS, LLC. Kaysville, Utah, USA, ncss.com/software/pass). Of note, with sequential testing of the co-primary endpoints, the study remains to be adequately powered with the addition of the total opioid consumption co-primary endpoint. A sample size of 50 participants in each arm will have adequate power (>90%) to detect non-inferiority with a margin of 21.2 IV morphine equivalents using a one-sided test with a common standard deviation of 25 and alpha of 0.025. The non-inferiority margin was determined by the clinically significant threshold of 10.6 mg in daily IV morphine equivalent dose [24], therefore, 21.2 morphine equivalent dose for over 2 days (0-48 hours).

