Intention to treat statistical analyses will be used to test the null hypothesis. Thus, if a patient has been randomized to the TEA arm of the trial and an epidural cannot be placed or cannot be used due to other circumstances (ie. persistent hypotension) the patient will receive the other elements of the ERAS multimodal pain bundle, which is consistent with our current clinical practice and that patient's data will be included in the dataset for the TEA arm in the final analysis. Additionally, in the event a participant wishes to drop out of the study prematurely postoperatively (ie. declines further blood/saliva collection and/or to fill out surveys), they will be allowed to do so and the data collected during their enrollment period will still be included in the dataset for their respective treatment arm unless they submit a formal written objection.

Secondary outcome variables:

T-tests or the nonparametric Mann-Whitney test will be used to compare normally and non-normally distributed data between the study arms. The log-rank test will be used to compare the time to (ROBF) as well as the time to postoperative diuresis to account for right censoring in which case no event (ROBF/diuresis) is observed within the observed time. A Poisson regression model will be used to compare the length of hospital stay. Chi-square tests will be used to compare the incidence of major postoperative complications between the two treatments. Chi-square tests will also be used to compare the incidence of major postoperative complications between the two treatments. Daily mean and median as well as mean baseline change in surgical stress biomarkers will be compared between treatment groups using t-tests or the Mann-Whitney test depending on whether data are normally or non-normally distributed. Average daily QoR-15 scores will be compared between the study cohorts.

b. Early stopping rules.

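### Length of stay is compared with a Poisson model and no stated variance correction, so its default p-value and interval are calibrated only if the variance of stay equals its mean

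*Combined protocol and SAP*

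**What the plan says.** Section 7 (Study Statistics), under Secondary outcome variables, gives length of stay its own method: "A Poisson regression model will be used to compare the length of hospital stay". That is the whole specification. It names no covariates, variance estimator, dispersion parameter or fallback model.

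The general rule in the same paragraph is "T-tests or the nonparametric Mann-Whitney test will be used to compare normally and non-normally distributed data between the study arms". It does not replace the Poisson model for length of stay, because that endpoint has a named method.

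Section 2 (Objectives), secondary measure 5, defines the endpoint and says that "length of hospital stay and time (in days) to meeting discharge criteria will be separately recorded". The reason given is "Often, patients remain inpatient beyond the time at which they first meet discharge criteria due to a variety of psychosocial factors".

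Neither section gives a mean, SD or variance for length of stay. No significance level is stated for secondary endpoints.

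**The concern.** A Poisson model fixes the variance at the mean. That can be a natural assumption for counts of independent events. Length of stay is a duration recorded in days, and nothing about it makes the two quantities equal.

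The protocol gives grounds for doubt in both directions. Psychosocial delay after readiness, and a mix of likely benign and likely malignant cases, can spread stays out. A single standardised ERAS pathway for all patients (section 4, Study Procedures) could pull them together. The protocol states the delay; the effects on the variance are inference.

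If the variance exceeds the mean, the default standard error is too small, chance differences are called significant too often, and the interval is too narrow. If the variance is below the mean, the reverse happens and a real difference can be missed. The comparison will attract interest because section 3 (Background) cites longer stay as one of the drawbacks of epidural analgesia.

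**Working it through.** **The plan's own figure.** The plan states no figure for length of stay. The only related number is the group size, which comes from the primary AUC calculation: "A group sample size of 50 per cohort is needed achieve a 90% power to detect non-inferiority using a one-sided, Mann-Whitney test". Its inputs are a margin of 38, an SD of 55, a true difference of 0 and a one-sided alpha of 0.025.

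- Normal test: n = 2 × (1.960 + 1.282)² × 55² / 38² = 44.02, so 45 per arm.
- Dividing by the Mann-Whitney efficiency 3/π: 45 / 0.955 = 47.1, so 48 per arm. A noncentral-t version also first reaches 90% at 48 (90.5%).
- Power at 50 per arm is 91.6% (noncentral t) to 92.2% (normal).

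The stated 50 per arm is therefore reproduced to within two patients. It is used below only as the group size.

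**Effect of the variance assumption.** Let μ be the mean stay, φ the variance-to-mean ratio and n the number per arm, with the same distribution in both arms under the null.

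- Model-based variance of the log ratio of means: 2 / (nμ).
- Actual variance (delta method): 2φμ / (nμ²) = 2φ / (nμ).
- The model-based standard error is therefore the true one divided by √φ.
- Actual type I error of a nominal two-sided 5% test: 2 × [1 − Φ(1.96 / √φ)].

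| Assumed φ | 1.96/√φ | Type I error | Coverage of 95% interval |
|---|---|---|---|
| 0.5 | 2.77 | 0.6% | 99.4% |
| 1 | 1.96 | 5.0% | 95.0% |
| 1.5 | 1.60 | 11.0% | 89.0% |
| 2 | 1.39 | 16.6% | 83.4% |
| 3 | 1.13 | 25.8% | 74.2% |

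The same formula with φ = SD²/mean, for assumed stays in days:

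- mean 4, SD 1.5 (φ = 0.56): 0.9%
- mean 4, SD 2 (φ = 1): 5.0%
- mean 5, SD 3 (φ = 1.8): 14.4%
- mean 5, SD 4 (φ = 3.2): 27.3%

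**Simulation check.** Each scenario used 20,000 null trials with 50 per arm.

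- Model-based Poisson standard error: negative binomial stays with mean 5 gave 16.4% at φ = 2 and 25.8% at φ = 3, in line with the formula. Lognormal stays with median 4 days, rounded up, gave 0.1%, 1.8%, 6.9% and 14.9% at log-SDs of 0.3, 0.4, 0.5 and 0.6. Skewed stays can therefore err in either direction.
- Robust (sandwich) standard error: 5.1% to 5.7% in every scenario, from φ of about 0.2 to 4.
- Quasi-Poisson standard error: 4.9% to 5.3% in the same scenarios.

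**The case against.** The strongest reply is that the plan says only that a Poisson regression model will be used. A Poisson model with robust standard errors is still a Poisson model, so this may be a missing detail rather than a wrong method. It is true that the plan does not rule out a robust variance. But it does not ask for one either, and a model followed as written yields its default standard error. Because the trial is unblinded, it is better to settle this choice before the results are seen.

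The second reply is that the error may be small. This stands. With mean 4 and SD 2 there is no error at all, and one skewed scenario gave 6.9%.

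A reader might infer more than the documents support:

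- **That the length-of-stay p-value will be wrong, or will be too small.** This depends on a variance that the documents do not give. Delay past readiness does not by itself show that the variance exceeds the mean.
- **That the protocol names ileus and complications as causes of long stays.** It lists them as separate endpoints. Only psychosocial factors are tied to a longer stay. A link through return of bowel function, which is a discharge criterion, is reasonable but is the reader's inference.
- **That days to meeting discharge criteria has the same problem.** The Poisson sentence does not cover that measure, and the general t-test or Mann-Whitney rule can.
- **That the trial's main conclusion is at risk.** Section 7 ties that conclusion to the two co-primary endpoints.

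**Conclusion.** The point holds in conditional form. As written, the length-of-stay test and interval are calibrated only if the variance equals the mean, and the plan neither justifies nor checks that condition. Exact equality would be a coincidence.

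The direction and size of any error are unknown. The range from 0.6% at a ratio of 0.5 to 26% at a ratio of 3 rests on assumed ratios, an assumed two-sided 5% level and equal distributions in the two arms. The point touches the standard error, p-value and interval of one secondary endpoint. The estimated ratio of mean stays remains valid, and the co-primary tests and the sample size are not affected. It is worth correcting because the remedy is simple and needs no knowledge of the true variance.

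**What to change.** In section 7, keep the log-link Poisson model for mean length of stay and state in advance that its standard errors, p-value and confidence interval will use a robust (sandwich) variance or a quasi-Poisson scale parameter. Either one works whether the variance is above or below the mean. A negative binomial model is not an equivalent choice: it cannot represent a variance below the mean, so it deals with overdispersion only. State the significance level for this comparison in the same place.

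The change costs one sentence and needs no extra data or patients. The log-scale interval changes width by √φ: about 22% wider at a ratio of 1.5 (√1.5 = 1.22), 41% at 2 (1.41) and 73% at 3 (1.73), and about 29% narrower at 0.5 (0.71). The widening could be substantial, but it is the correct width. With 50 per arm the sandwich version may run slightly above nominal (up to 5.7% in simulation).

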be isolated and banked in [name] laboratory for ELISA by his research team and the SOM Onc Human Immunology Core in order to measure circulating levels of ACTH, epinephrine, total cortisol, ADH, interleukins, ANP, syndecan-1, glycosaminoglycans, endothelial glycocalyx constituents, CRP and TNF- α . Saliva (1mL) will also be collected by patients at 6PM preoperatively and at 6PM \pm 1hr postoperatively thereafter through the first 7 days after surgery for cortisol measurement by ELISA since measurements of salivary cortisol more accurately reflect serum free cortisol concentrations than do measurements of serum total cortisol. Saliva collection on postoperative day 0 is optional and mandatory on postoperative days 1-7. The salivary collection protocol has previously been published.¹⁰

3. Background (briefly describe pre-clinical and clinical data, current experience with procedures, drug or device, and any other relevant information to justify the research)

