- c. Justification and safety information if non-FDA approved drugs without an IND will be administered.

7. Study Statistics

- a. Primary outcome variables:

The study has two co-primary endpoints: (1) the mean Area under the Curve (AUC) of visual analog scale (VAS) pain intensity scores from 0 to 48 hours postoperatively and (2) total opioid consumption (IV morphine equivalents, mg) from 0 to 48 hours postoperatively. The primary hypothesis will be assessed in joint hypothesis testing which controls the type I error at 0.025 across both non-inferiority tests; AUC for VAS pain scores and total opioid consumption through 48 hours postoperatively. Significance will need to be achieved for both co-primary endpoints.

For analyzing the AUC of the VAS pain assessment, we will use an approach that has been previously used in Pacira studies. The area under the curve (AUC) is derived using the trapezoidal rule (see formula below) using the adjusted and imputed VAS pain scores. The VAS scores will be adjusted for the use of rescue medication using the WWOCF approach. AUC will start with the first postsurgical pain assessment. All pain assessments through 48 hours after surgery, including both scheduled and unscheduled will be used in deriving AUC. Exact assessment times will be used in deriving AUC.

$$AUC = \left\{ \sum_{i=2}^n (p_i + p_{(i-1)})(t_i + t_{(i-1)}) \right\} / 2$$

The AUC for VAS may be analyzed using ANOVA with treatment group as a main effect and include other covariates as deemed reasonable. Based on the model, the LS Mean and SE will be reported for each treatment group. The 95% confidence interval for the difference between

treatment groups and the one-sided test performed at 2.5% level of significance will be inspected for non-inferiority.

Total opioid consumption over 48 hours postoperatively will be abstracted by our research assistant from the medical administration record (MAR) as it appears in the EMR for each patient.

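### Stress biomarkers are compared by unadjusted tests although a preoperative value is already planned, and no governing day or scale is named for each biomarker

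*Combined protocol and SAP*

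**What the plan says.** Section 7 (Study Statistics), under the secondary outcome variables, gives the whole biomarker analysis in one sentence. Daily means and medians are compared between the arms, and "mean baseline change in surgical stress biomarkers will be compared between treatment groups using t-tests or the Mann-Whitney test", the choice of test depending on distribution. It names no covariate, no longitudinal model, no governing day or scale, and no multiplicity rule.

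The baseline is set out under Translational Endpoints in section 2. Blood "will be collected on the DOS when routine IV access is established in preop or the operating room", and saliva "will also be collected by patients at 6PM preoperatively". Both continue daily to day 7 (for blood, "postoperative days 1 through postoperative day 7"). A separate sentence says "Blood collection on postoperative day 0 is optional". Section 4a repeats this schedule and adds that no extra IV access will be requested for blood.

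Section 7 permits covariates only for the two co-primary endpoints. For pain it says "The AUC for VAS may be analyzed using ANOVA with treatment group as a main effect and include other covariates as deemed reasonable", and there is similar ANCOVA wording for opioid consumption. Neither statement extends to the biomarkers.

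**The concern.** Whether epidural analgesia and liposomal bupivacaine differ in their effect on the stress response is part of the stated project goal. Section 3 gives the belief that epidurals reduce that response better as the reason the institution prefers them. Three features of the planned analysis weaken the answer.

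- **Precision.** A comparison of raw daily levels makes no use of the preoperative value. A change score uses it with a fixed coefficient of 1. A model would estimate the coefficient from the data.
- **No governing result.** Each biomarker can be tested on several days and on two scales. These results may disagree, and nothing says which one counts.
- **Who contributes later blood samples.** Draws coincide with routine access and there are no extra outpatient visits, so discharged patients may have no later blood values. Section 3 cites evidence that epidurals lengthen stay, and length of stay is itself compared between arms. The patients left in the later-day blood comparisons could therefore differ by arm.

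**Working it through.** **The plan's own figure.** No sample size or power is stated for the biomarkers. The 50 per arm in section 7 is for the pain AUC (margin 38, SD 55, one-sided 0.025, 90% power). A normal approximation gives 45 per arm. Dividing by the Mann-Whitney efficiency for normal data, 45 / 0.955 = 47.1, gives 48, close to 50. This supplies the group size used below and says nothing about the size of the biomarker point.

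**Inputs.** 50 per arm is from section 7. The documents do not give the correlation rho between the preoperative and postoperative values, or the ratio k of postoperative to preoperative SD. Both are assumptions here.

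**Formulas for one postoperative day.** These are variances of the between-arm difference in means, relative to the raw level. They describe the t-test form of the plan directly and are only a guide for Mann-Whitney.

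- Raw level: 1
- Change score: (k² + 1 − 2·rho·k) / k², which is 2(1 − rho) when k = 1
- Baseline as covariate: 1 − rho², times 1 + 1/96 at 50 per arm for estimating the slope (about 1%)

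The raw level exceeds the adjusted variance by rho², and the change score exceeds it by (1/k − rho)². Neither quantity can be negative, so apart from the 1% adjustment never loses to either planned comparison.

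**Equal SDs (k = 1).** The power columns assume a true difference of 0.5 SD and a two-sided 5% test, and include the 1%.

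| rho | Change / raw | Adjusted / raw | Adjusted / change | Power: raw | Power: change | Power: adjusted |
|---|---|---|---|---|---|---|
| 0.3 | 1.40 | 0.91 | 0.65 | 0.705 | 0.561 | 0.741 |
| 0.5 | 1.00 | 0.75 | 0.75 | 0.705 | 0.705 | 0.819 |
| 0.7 | 0.60 | 0.51 | 0.85 | 0.705 | 0.898 | 0.936 |

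At rho = 0.2, adjusted / raw is 0.96, a gain of only 4%.

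**Unequal SDs, rho = 0.5 (adjusted / raw = 0.75 throughout).**

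- k = 1: change / raw = 1.00
- k = 2: (4 + 1 − 2) / 4 = 0.75, so there is no gain over change
- k = 3: (9 + 1 − 3) / 9 = 0.78, so change has about 4% more variance than adjustment (0.78 / 0.75)

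**Number of possible tests.** Section 2 lists 11 blood analytes or classes, and salivary cortisol makes 12. If each is tested on 7 days and on 2 scales, 12 × 7 × 2 = 168 tests. With no true effects, 168 × 0.05 = 8.4 would be expected to reach 5%. The 12 is an assumption: some entries are open classes (interleukins, for example), and section 4a adds serum glucose. Section 7 also does not say that change is tested on every day.

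**The case against.** The strongest reply is that this is an efficiency refinement for endpoints with no power statement, alpha allocation or decision rule. Under randomisation, neither planned comparison is biased by the way it treats baseline. That is correct, and it limits the weight of the point.

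The reply also rightly blocks several stronger readings that a reader might infer:

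- *That baseline is ignored.* It is not, because it enters the planned change analysis. What is missing is its use as a covariate.
- *That change scores always over-correct, or that adjustment is worth one third more patients than either planned test.* The first needs a baseline slope (rho × k) below 1. The second needs rho = 0.5 and equal SDs. At rho = 0.5 and k = 2 the slope is exactly 1 and nothing is gained over change; at k = 3 the slope is 1.5 and change under-corrects. Equal SDs cannot be taken for granted for markers chosen because surgery perturbs them, although a log scale may bring the SDs closer.
- *That all later-day biomarker data are selected by length of stay.* The documents support this only for blood. Saliva is collected by patients, is mandatory on days 1 to 7, and has no stated inpatient restriction. No expected length of stay is given, so the extent for blood is unknown.
- *That a mixed model removes the selection.* It adds no late samples. It uses the earlier values of discharged patients and relies on data being missing at random.

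What survives is that the covariate is already planned, adjusting for it costs essentially nothing in precision, and no result is named as the one that counts.

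**Conclusion.** The point holds as a limited, inexpensive improvement. Baseline adjustment is never less precise than either planned comparison of means, apart from about 1%. The size of the gain cannot be fixed from the documents. Against the raw level the variance falls by 9%, 25% or 49% at assumed rho of 0.3, 0.5 or 0.7. Against change it falls by 35%, 25% or 15% at the same values if the SDs are equal, and possibly by nothing if postoperative SDs are larger.

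The lack of a governing day and scale is clear from the text. The figure of 168 tests is one reading under stated assumptions, not a documented count, and conflicting results are a possibility rather than a certainty. Selection by hospital stay is plausible for later blood samples and is not shown for saliva. The consequences are confined to the translational endpoints; nothing here changes the co-primary non-inferiority conclusions.

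**What to change.** In section 7, under the secondary outcome variables, replace the unadjusted biomarker tests with a baseline-adjusted analysis for each biomarker, on the log scale where skewed. Use the preoperative value and the malignancy stratum, already a randomisation factor, as covariates. Preferably fit one repeated-measures model over postoperative days 1 to 7 with arm, day and arm-by-day terms, and treat salivary cortisol in the same way.

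Name one arm contrast per biomarker in advance (an average over days 1 to 3 is one possibility) and show the daily estimates descriptively. State the missing-at-random assumption for blood after discharge. Make clear that the baseline is the preoperative sample and not the optional postoperative day 0 sample, because a missing baseline would weaken the change analysis and the adjusted analysis alike.

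The cost is a change of SAP wording and a little more analysis work. No new samples are needed.

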In addition, an efficacy interim analysis for the primary outcome will be carried out when 20 patients are enrolled in each group. The results will be provided to the DSMB committee to determine whether one method is truly inferior to the other before enrollment continues (see section on Early stopping rules below). The determination will be based on comparing the average AUC of VAS for 0-48 hours postoperative. Of the two co-primary endpoints, equivalent pain intensity scores is harder to achieve and is the more clinically relevant one. Interim analysis of toxicity, outcome and ongoing scientific investigations will be performed at least annually by the Sidney Kimmel Comprehensive Cancer Center Data Safety Monitoring Board (SKCCC DSMB). The SKCCC DSMB Recommendation letter will state the timeline for the next required review. The SKCCC DSMB will review aspects of this trial that are outlined in the responsibilities section of the Data and Safety Monitoring Board (DSMB) Guidance. If the committee decides that amendments should be made to this trial, recommendations will be made in writing to the Study Principal Investigator. The study team will submit modifications to the IRB within 60 days of receipt from the DSMB. The Associate Director of Clinical Research, will arbitrate any disagreements between the DSMB and the study Principal Investigator. These changes may include early termination of accrual if deemed appropriate. The SKCCC Compliance Monitoring Program will provide external monitoring for JHU-affiliated sites in accordance with SKCCC DSMP (Version 6.0, 02/21/2019). The SMC Subcommittee will determine the level of patient safety risk and level/frequency of monitoring.

b. Study duration and number of study visits required of research participants.

Patients will be considered to be "on study" for the duration of their inpatient hospitalization and for 14 days postoperatively. Each participating individual will have no extra or additional outpatient study visits.

c. Blinding, including justification for blinding or not blinding the trial, if applicable.

Because of the invasive nature of the interventions, neither the trial participants nor the investigators will be masked to group allocation.

d. Justification of why participants will not receive routine care or will have current therapy stopped.

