If there is concern for harm on either arm of the study this will be immediately discussed with the PI and the study will be stopped until the concern is resolved. The PI will internally monitor the progress of the trial, including review and confirmation of all safety/treatment-related outcomes, response assessments, safety reports and/or any related source documentation. As per above, the DSMB will meet after 20 patients have been enrolled in each arm. Regarding the futility boundary for the interim analysis – based on the results from the pilot study in 2019, the pain for the Epidural group and for the Exparel group are about the same (3.9 vs 4.0 in a 0-10 scale). With the O'Brien-Fleming futility boundary of 0.2986, there is only 0.1% chance of falsely crossing the futility boundary and stopping the study at 20 participants per arm assuming equal pain for both groups. The overall power remains to be over 90%. If in case that the Exparel group is truly inferior to the Epidural group by at least the pre-specified non-inferiority margin, there is at least a 38% chance of claiming early futility at 20 patients per arm to protect more patients from being exposed to the inferior treatment.

Interim analysis of toxicity, outcome and ongoing scientific investigations will be performed at least annually by the Sidney Kimmel Comprehensive Cancer Center Data Safety Monitoring Board (SKCCC DSMB). The SKCCC DSMB Recommendation letter will state the timeline for the next required review. The SKCCC DSMB will review aspects of this trial that are outlined in the responsibilities section of the Data and Safety Monitoring Board (DSMB) Guidance. If the committee decides that amendments should be made to this trial, recommendations will be made in writing to the Study Principal Investigator. The study team will submit modifications to the IRB within 60 days of receipt from the DSMB. The Associate Director of Clinical Research, will arbitrate any disagreements between the DSMB and the study Principal Investigator. These changes may include early termination of accrual if deemed appropriate. The SKCCC Compliance Monitoring Program will provide external monitoring for JHU-affiliated sites in accordance with SKCCC DSMP (Version 6.0, 02/21/2019). The SMC Subcommittee will determine the level of patient safety risk and level/frequency of monitoring.

1. Risks

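### The futility boundary of 0.2986 lacks a test statistic and sign, and its 0.1% false-stop chance does not follow from the plan's AUC inputs (about 0.65%)

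*Combined protocol and SAP*

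**What the plan says.** Section 4a plans an interim look once 20 patients are enrolled in each group. It calls this an efficacy analysis, says the DSMB will use it "to determine whether one method is truly inferior to the other before enrollment continues", and names the endpoint: "The determination will be based on comparing the average AUC of VAS for 0-48 hours postoperative". For the rule itself it refers to the early stopping section.

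Section 7b gives that rule, an O'Brien-Fleming "futility boundary of 0.2986, there is only 0.1% chance of falsely crossing the futility boundary and stopping the study". The condition attached is "stopping the study at 20 participants per arm assuming equal pain for both groups". It then says of power, "The overall power remains to be over 90" percent, and of a truly inferior LB arm, "there is at least a 38% chance of claiming early futility at 20 patients per arm". No test statistic, sign or SD is given for the boundary.

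The design inputs are in Section 7a: AUC margin 38, true difference 0, one-sided alpha 0.025, 50 per arm, a Mann-Whitney test, and "the data are drawn from populations with standard deviations of 55.0". The same section gives a margin of 21.2 and SD of 25 for the opioid endpoint.

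**The concern.** A stopping rule has to be applied from the page. The number 0.2986 could be a Z value of either sign, a p-value, or a conditional power, and these lead to different decisions on the same data. The operating figures printed beside it should settle the matter, but they do not agree with each other on the plan's AUC inputs: the reading that gives 38% does not give 0.1%.

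At stake are the observed difference at which the DSMB would stop, and the risk it is told it runs of stopping a trial of two equally effective treatments.

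**Working it through.** **Inputs.** Margin 38, SD 55, true difference 0, one-sided alpha 0.025, 50 per arm (Section 7a); 20 per arm at the interim (Sections 4a and 7b); boundary 0.2986 (Section 7b).

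**Final design first.** The standard error at 50 per arm is 55 × √(2/50) = 11.0. Power is Φ(38/11.0 − 1.96) = Φ(1.495) = 93.2%, so the 90% claim is met by normal approximation.

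**Interim statistic.** Let Z = (38 − D)/SE, where D is mean AUC for LB minus mean AUC for epidural.

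- SE = 55 × √(2/20) = 17.39.
- Mean of Z if pain is equal: 38/17.39 = 2.185.
- Mean of Z if LB is worse by exactly the margin: 0.
- Probability of stopping at Z ≤ b: Φ(b − mean of Z).

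**Reproducing the 38%.** Φ(−0.2986) = 38.3%. This is the stated figure and it requires b = −0.2986. It does not depend on the SD. An O'Brien-Fleming-type beta-spending calculation with beta 0.10 at information 20/50 = 0.4 gives a boundary of −0.293 (non-binding) or −0.296 (binding), which supports the negative sign.

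**Testing the 0.1%.** With b = −0.2986 and equal pain, Φ(−0.2986 − 2.185) = Φ(−2.483) = 0.65%. A t test gives 0.66%. A simulation of the Mann-Whitney statistic with normal data (400,000 trials) gives 0.76%. At the pilot difference of 0.1 VAS points (0.1 × 48 = 4.8 AUC units) the normal calculation gives 1.4%.

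**Other readings on the AUC inputs:**

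| Stop when | Observed difference that stops | False stop, equal pain | Stop at the margin |
|---|---|---|---|
| Z ≤ −0.2986 | 38 + 0.2986 × 17.39 = 43.2 or more | 0.65% | 38% |
| Z ≤ +0.2986 (sign as printed) | 38 − 0.2986 × 17.39 = 32.8 or more | 3.0% | 62% |
| One-sided non-inferiority p > 0.2986 | above about 28.8 | 4.9% | 70% |
| Conditional power under the design effect below 0.2986 | not calculated | 0.13% | 20% |
| Section 7b states | not given | 0.1% | at least 38% |

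No row matches both stated figures.

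**What would give 0.1%.** Keeping b = −0.2986, the mean of Z under equal pain would have to be 3.090 − 0.299 = 2.792. Then SE = 38/2.792 = 13.61 and SD = 13.61/√(2/20) = about 43. Allowing for rounding to 0.1%, SDs of about 40 to 45 would do. With SD 55, about 33 per arm would be needed at the interim. With SD 55 and 20 per arm, the boundary would have to be near −0.905, which stops only 18% of the time at the margin.

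**Opioid inputs.** SE = 25 × √(2/20) = 7.906, and 21.2/7.906 = 2.682. Then Φ(−0.2986 − 2.682) = 0.14%, with 38% at the margin.

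**Overall power.** With the look at −0.2986 and a final critical value of 1.96, power is 93.0% (91.7% with +0.2986). The claim of power above 90% holds either way.

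**The case against.** The case for leaving this alone has several parts, and most of them limit the point.

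- A reader might infer that the boundary has no direction. It has one. Section 7b ties early futility to LB being the inferior arm, and Section 7a says the margin is an increase in pain. Only the statistic and sign convention are missing, and the 38% lets a careful reader recover them.
- A reader might infer that no reading can give both 38% and 0.1%. That is too strong. An SD of about 43 does so, and the opioid inputs give 38% and 0.14%. Section 7b mentions the 2019 pilot and does not say that SD 55 was used. However, no pilot SD is reported, and Section 4a places the interim look on the AUC. So the 0.1% either rests on an unstated input or is wrong.
- The absolute gap is small, and a futility-only stop does not inflate the type I error. Both are true.
- A reader might infer from Section 4a an efficacy stop, in either direction, without alpha control. The documents do not support that. Section 4a defers to the early stopping section, which contains only a futility boundary, and efficacy there can mean the efficacy endpoint. The wording is loose rather than a second stopping rule.

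What survives is that a DSMB should not have to work backwards from one operating figure to learn that the printed sign is the reverse of the likely rule, when another operating figure beside it does not fit.

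**Conclusion.** Wrong as written, and minor. On the plan's AUC inputs, the rule that yields the stated 38% has a false-stop chance of about 0.65% under equal pain (about 0.8% for Mann-Whitney), some 6.5 times the stated 0.1% but only 0.55 percentage points more. The missing sign matters somewhat more: it moves the stopping threshold between about 43.2 and 32.8 AUC units.

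This rests on SD 55, 20 evaluable patients per arm, approximately normal data, and the negative non-inferiority Z scale, which is inferred from the 38% and from the beta-spending check rather than stated. It should not be read as a failure of the design. The sample size, the 38%, power above 90%, and the final one-sided alpha of 0.025 all hold.

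**What to change.** In Section 7b, the study statistician should:

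- define the interim statistic and its null, for example Z = (38 − [mean AUC LB − mean AUC epidural])/SE, and say whether it is the mean-based or the Mann-Whitney version;
- confirm that stopping applies at Z ≤ −0.2986, and give the equivalent observed difference (about 43.2 units at SD 55) and the information fraction (20/50 = 0.4);
- replace 0.1% with about 0.7%, or with the figure for the test chosen, or else state the different SD from which 0.1% was obtained;
- keep the 38% and the statement on power.

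In Section 4a, describe the look as futility only, for LB worse than epidural, with no efficacy claim and the final one-sided alpha unchanged at 0.025.

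The cost is wording in two sections and in the instructions given to the DSMB, plus one slightly less favourable operating figure. Sample size, procedures and final analysis do not change. It should be settled before the look at 20 per arm.
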